## Metabolic Laboratory Parameters

Administration of TDF has been associated with lower fasting low-density lipoprotein (LDL) and high-density lipoprotein (HDL) as compared with other antiviral agents. As plasma TFV exposures are approximately 90% lower with TAF administration than with TDF, fasting lipid concentrations remained relatively stable through Week 48 in the TAF treatment group, while TDF administration resulted in the expected lipid-lowering TFV effect, with decreases from baseline in fasting lipid parameters observed in the TDF group. Median decreases from baseline in total cholesterol, LDL, HDL, and triglycerides were greater in the TDF group than the TAF group, with TDF subjects demonstrating reductions in all parameters at Week 48. The difference between groups in median change from baseline was statistically significant a Week 48 for total cholesterol, direct LDL, HDL, and triglycerides ( $p < 0.001$ ). Median (Q1, Q3) changes from baseline at Week 48 for fasting lipid parameters were as follows:

- **Total cholesterol:** TAF -2 (-17, 17) mg/dL; TDF -24 (-42, -6) mg/dL
- **LDL:** TAF 4 (-9, 20) mg/dL; TDF -9 (-25, 5) mg/dL
- **HDL:** TAF -3 (-10, 2) mg/dL; TDF -9 (-17, -3) mg/dL
- **Triglycerides:** TAF 6 (-13, 26) mg/dL; TDF -7 (-27, 10) mg/dL

The median (Q1, Q3) change from baseline at Week 48 in total cholesterol to HDL ratio was 0.2 (-0.1, 0.5) in the TAF group and 0.2 (-0.2, 0.5) in the TDF group (p = 0.16 for the difference between treatment groups).

Eight subjects (0.9%) in the TAF group had Grade 3 elevated fasting cholesterol; 7 of the 8 subjects had a history of hyperlipidemia and/or elevated fasting cholesterol at baseline. There were no subjects with Grade 4 elevated fasting cholesterol in the TAF group, and none with Grade 3 or 4 elevated fasting cholesterol in the TDF group. Thirty-seven subjects (4.4%) in the TAF group and 1 subject (0.2%) in the TDF group had Grade 3 elevated fasting LDL. Overall, changes in median values of total cholesterol, LDL, HDL, and triglycerides in the TAF group were not clinically relevant, and none of the subjects with Grade 3 elevations in fasting lipids had clinical AEs associated with lipid abnormalities.

Please refer to the latest version of the Investigator's Brochure for TAF for further information on the clinical program.

#### **1.4. Rationale for This Study**

Given the low rate of HBsAg loss with currently available therapies and the treatment burden associated with life-long treatment to maintain viral suppression, there is a need to identify new therapies that may provide durable HBsAg loss with a finite treatment duration. The primary objective is to evaluate the safety, tolerability and efficacy of GS-9992 in association with an oral nucleotide (NUC) HBV polymerase inhibitor (TAF or other commercially available NUC) for the treatment of CHB subjects, while also evaluating the changes in HBV specific immune responses following treatment with GS-9992.

This Phase 2 study will be conducted in subjects with CHB, who are currently not receiving treatment for CHB (can be either treatment naïve or previously treated) or are virally-suppressed on a commercially available oral NUC. Viremic subjects with CHB generally have a rapid decline in viremia in response to beginning antiviral treatment. The decrease in viral burden may allow for an increased responsiveness to immune stimulation and forms the basis for the design of Groups 1-3 and 5 in this study. To further evaluate GS-9992 ability to improve immune response, an additional group, Group 4, will enroll virally-suppressed CHB subjects on a commercially available NUC. The immune responsiveness of CHB patients has been shown to improve in patients who are on chronic suppressive antiviral therapy with less antigen burden. Virally-suppressed patients will have lower levels of HBV virions and proteins, including HBsAg, within the serum as well as lower expression of HBV antigens within infected hepatocytes. Therefore Group 4 will evaluate the potential maximal efficacy benefits of GS-9992 in virally-suppressed CHB subjects.

Further, the safety data with GS-9992 in treatment naive subjects and in virally-suppressed subjects was evaluated in a Phase 1b study SBP-9200-101 and in the ongoing Phase 2 study SBP-9200-HBV-201. Both studies support the evaluation of GS-9992 in these populations. Subjects will be stratified by HBeAg status. HBeAg status has been shown in prior studies of TDF (GS-US-174-0102 and GS-US-174-0103) to be a predictor of eventual HBsAg loss with TDF treatment irrespective of HBV genotype.

#### **1.4.1. Rationale for Dose Selection**

##### **GS-9992 for Groups 1-4**

In a 3-month, repeat-dose toxicology study conducted in rat (50, 150, and 250 mg/kg/day) and monkey (15, 30, and 60 mg/kg/day), the NOAEL was determined to be 250 mg/kg for the rat and 15 mg/kg for the monkey. Thus, monkey was considered to be the most sensitive species and was used to designate the minimum recommended starting dose (MRSD) for clinical studies. The NOAEL in humans corrected for body surface area (equation 1) using the NOAEL from monkey (15 mg/kg) and the mean body weight of the monkeys in that dose group (2.9 kg) resulting in a human equivalent dose (HED) for the human equivalent NOAEL of 3.43 mg/kg. To allow for a 10-fold safety margin, a dose of 0.34 mg/kg was selected as the MRSD. This is equivalent to a dose of 24 mg to a 70 kg human. Thus, the starting dose for the clinical study in HBV patients is proposed to be 25 mg (or 0.36 mg/kg).

Equation 1:  $HED = (\text{animal dose in mg/kg} * \text{body weight in kg})^{0.33}$

The MRSD chosen for the proposed clinical study is 25 mg to be incrementally increased up to 400 mg. These doses are expected to be effective against HBV in patients, based upon nonclinical studies. A dose of 9 mg/kg administered to a woodchuck model of hepatitis for 4 weeks was efficacious against hepatitis B infection as assessed by a decline in HBV DNA. In a subsequent study, a dose of 15 mg/kg/day for 12 weeks resulted in dose and time-related decline in HBV viral DNA that was at or near baseline values at the end of the study. In a transgenic HBV mouse model, a dose of 10 mg/kg produced statistically significant decline in HBV DNA. By correcting for body surface area, the human equivalent efficacious dose calculated from woodchuck efficacy studies ranged from 2.5 to 5 mg/kg (mean body weight 2.8 kg). The human equivalent efficacious dose calculated from the murine efficacy studies was 0.62 mg/kg (mean body weight of 0.034 kg). Since the proposed doses in the clinical study range from 25 mg up to 400 mg or 0.36 to 5.76 mg/kg in a 70 kg patient, it is reasonable to expect that this dose range will be therapeutically effective in HBV patients.

In the ongoing Phase 2 ACHIEVE trial, all subjects in Cohorts 1,2, 3, and 4 (n = 20/ cohort) have completed treatment with GS-9992 (SB 9200) 25 mg, 50mg, 100mg, and 200mg once daily monotherapy for 12 weeks. There were no clinical, hematological or biochemical SAEs and all AEs were graded mild to moderate in severity.

There were no interferon-like side effects, except for 3 subjects with mild AE of flu-like symptoms in Cohort 3, 1 of the 3 subjects was administered placebo. There were no dose proportional increases in the number or severity of treatment-emergent adverse events reported.

Overall, 6 subjects experienced an ALT flare >200 IU/mL, 2 subjects were on placebo; no subjects have met Hy's law.

GS-9992 50 mg and 100 mg monotherapy for 12 weeks demonstrated a mean change in HBV DNA of  $-0.61 \log_{10}$  IU/mL and  $-0.55 \log_{10}$  IU/mL in HBeAg positive subjects, respectively, and  $-1.05 \log_{10}$  IU/mL and  $-2.26 \log_{10}$  IU/mL in HBeAg negative subjects, respectively. The mean change in HBV RNA decline at week 12 was  $-0.46 \log_{10}$  IU/mL and  $-0.49 \log_{10}$  IU/mL in HBeAg positive and  $-3.15 \log_{10}$  IU/mL and  $-3.2 \log_{10}$  IU/mL in HBeAg negative subjects administered GS-9992 50 mg and 100 mg, respectively.

The safety and efficacy results from the Phase 2 ACHIEVE trial support further evaluation of the 50 mg and 100 mg dose of GS-9992 in combination with a NUC in this study. The 200mg GS-9992 monotherapy for 12 weeks is currently being evaluated in Cohort 4 in the ACHIEVE trial. Safety of the 200mg GS-9992 monotherapy has been confirmed by ACHIEVE trial's independent Data Safety Monitoring Board. To date, no safety concerns have been observed.

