In a GLP 39-week oral gavage toxicity study, cynomolgus monkeys were administered inarigivir at doses of 0, 5, 10, 15, or 20 mg/kg/day for 39 weeks or at doses of 30 or 60 mg/kg three times weekly for 39 weeks. In animals that survived their scheduled termination, the oral administration of SB 9200 once daily at doses of 5, 10, 15, and 20 mg/kg/day or tri-weekly at 30 mg/kg/day was well tolerated and did not result in any signs of overt toxicity. Microscopic changes in animals administered tri-weekly at 30 mg/kg/day were noted in the liver, which included minimal hepatocellular single cell necrosis and minimal mixed cell infiltrate in 7/8 animals, and minimal intracellular hemosiderin pigment in 1/8 animals. However, there were no adverse events found in animals administered doses at or lower than 20mg/kg/day, therefore the

NOAEL in this study was judged to be 20 mg/kg/day. This study is still in the reporting phase and the toxicokinetic parameters have not yet been reported. However, the microscopic findings in the liver at 30 mg/kg dosed TIW was consistent with previous studies and lack of findings at 20 mg/kg/day was similar to the results in the 13 week study in cynomolgus monkeys where no findings were observed at the 15 mg/kg/day dose level.

Additional details of the nonclinical studies for GS-9992 are provided in the Investigator's Brochure (IB) for SB 9200.

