*In vivo* pharmacology studies following IP injection of 100 mg/kg/day showed significant reduction of viral DNA load in the liver of transgenic mice, with antiviral activity similar to that of adefovir.

The minimally effective dose in this model was 1 mg/kg. Similar studies conducted with oral SB 9200 showed the minimal effective dose to be between 1 and 10 mg/kg. Other, in vivo studies in naturally infected (WHV) woodchucks showed induction of RIG-1 in liver biopsies after 12 weeks treatment, with dose-dependent activity following 12 weeks of 15 and 30 mg/kg/day resulting in reduced surface antigen and serum WHV DNA; delayed viral relapse at higher dose; elevated IFN, RIG-1, NOD2; and significant reductions in hepatic viral DNA, RNA, cccDNA. Although the pharmacokinetics of SB 9000 were not measured in the pharmacology studies, the lowest doses of SB 9200 shown to have efficacy in these pharmacology models were 10 mg/kg/day in the mouse and 15mg/kg in the woodchuck, on the basis of body surface area, the human equivalent doses of either the mouse or the woodchuck would be adequately covered by a 400 mg/day dose in humans.

The pre-clinical and clinical profile of inarigivir supports its exploration as a potential treatment option for patients with HBV at 400 mg. The pre-clinical toxicology studies have consistently indicated that the monkey is the more sensitive species and that the liver is the sole target organ of inarigivir mediated toxicity. The exposure parameters Cmax and AUC(0-t) at the identified NOAEL in the longest term completed GLP toxicology study are 3.5 and 1.7-fold higher respectively than those observed when 400 mg was administered in the clinic. In all of the clinical studies conducted so far where doses between 25 and 900 mg have been administered daily for durations between 7 days and 12 weeks, the safety profile has been acceptable and there have been no changes in liver safety parameters that were independently associated with inarigivir, instead the changes in liver enzyme levels to date have been correlated with immune flares consistent with an ongoing HBV infection.

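### Does the faulty human-equivalent dose equation in protocol 1.4.1 call for a change to the trial plan?

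*Protocol*

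**What the plan says.** The part of protocol 1.4.1 on Groups 1-4 says the monkey NOAEL was converted by a body-surface correction, labelled Equation 1. The inputs are described in these words: "using the NOAEL from monkey (15 mg/kg) and the mean body weight of the monkeys in that dose group (2.9 kg"). Equation 1 multiplies the "animal dose in mg/kg" by body weight in kg and raises the product to the power 0.33. The outcome is then reported as follows: "resulting in a human equivalent dose (HED) for the human equivalent NOAEL of 3.43 mg/kg". A ten-fold margin then gives 0.34 mg/kg, 24 mg for a 70 kg person, and a proposed 25 mg starting dose.

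The same text describes woodchuck studies at 9 and 15 mg/kg and a mouse model at 10 mg/kg. Its woodchuck conversion, also attributed to body surface, is given thus: "human equivalent efficacious dose calculated from woodchuck efficacy studies ranged from 2.5 to 5 mg/kg (mean body weight 2.8 kg"). For the mouse it gives 0.62 mg/kg at 0.034 kg. The dose range is put at "25 mg up to 400 mg or 0.36 to 5.76 mg/kg in a 70 kg patient".

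The Group 5 part of 1.4.1 uses body surface area for efficacy: "the human equivalent doses of either the mouse or the woodchuck would be adequately covered by a 400 mg/day dose in humans". For safety it turns to plasma exposure and says of Cmax and AUC: "at the identified NOAEL in the longest term completed GLP toxicology study are 3.5 and 1.7-fold higher respectively". The comparison is with 400 mg in the clinic.

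Section 1.2.3 gives two monkey NOAELs that bear on this: 15 mg/kg/day at 13 weeks and 20 mg/kg/day at 39 weeks. Of the 39-week study it says: "This study is still in the reporting phase and the toxicokinetic parameters have not yet been reported".

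**The concern.** A body-surface conversion should scale the animal dose by a ratio of animal to human weight, so that doubling the animal dose doubles the human equivalent. Equation 1 does neither. The section also seems to convert in two ways. At nearly equal weights (2.9 and 2.8 kg), 15 mg/kg becomes 3.43 mg/kg for the monkey, while the woodchuck range reaches 5 mg/kg.

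What would be at stake is the safety argument for the highest dose. The 3.43 mg/kg figure is the only human-equivalent NOAEL the protocol states as a dose, and the liver is named as the sole target organ. Set beside 3.43 mg/kg, 400 mg lies above the human-equivalent NOAEL, whereas the exposure ratios place it below. The Group 5 text shows only the exposure comparison, and section 1.5 quantifies neither.

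**Working it through.** **Inputs** (protocol 1.4.1 unless stated): monkey 15 mg/kg, 2.9 kg; woodchuck 9 and 15 mg/kg, 2.8 kg; mouse 10 mg/kg, 0.034 kg; human 70 kg; exponent 0.33. The 39-week NOAEL of 20 mg/kg/day is from 1.2.3.

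**1. The printed figure.** Equation 1 gives (15 × 2.9)^0.33 = 3.47 mg/kg, 1.3% above the printed 3.43. With 2.8 kg, the woodchuck weight, it gives 3.43. The printed value therefore came from an equation of this form, and a fault in text extraction is unlikely.

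**2. Proportionality.** 2^0.33 = 1.26, so doubling the animal dose raises the result by only 26%.

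**3. One method or two?** Weight-ratio scaling, dose × (animal weight/70)^0.33, is an assumption here. The protocol does not print it.

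| Animal dose | Printed, mg/kg | Equation 1 | Weight ratio, 70 kg |
|---|---|---|---|
| Monkey 15 mg/kg | 3.43 | 3.47 | 5.25 |
| Woodchuck 9 mg/kg | range 2.5 to 5 | 2.90 | 3.11 |
| Woodchuck 15 mg/kg | range 2.5 to 5 | 3.43 | 5.19 |
| Mouse 10 mg/kg | 0.62 | 0.70 | 0.81 |

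Equation 1 cannot give the woodchuck range. A two-fold range of results needs a 2^(1/0.33) = 8.2-fold range of doses, and 15/9 is 1.67-fold. Even the 30 mg/kg mentioned in the Group 5 text gives only 4.31. Weight-ratio scaling comes near the upper woodchuck figure but misses the lower one and the mouse. Neither method reproduces the section. The protocol also does not match particular woodchuck doses to the ends of the range, so pairing 15 with 5 mg/kg is an inference.

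**4. Dose range.** 400/70 = 5.71 mg/kg. The printed 5.76 is 16 × the rounded 0.36, a 0.8% carry-over.

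**5. 400 mg against the NOAEL.** On the printed figure, 3.43 × 70 = 240 mg and 400/240 = 1.67. Under the assumed scaling at 70 kg, 5.25 mg/kg is 367 mg and 400/367 = 1.09. For human weight W, the ratio is (400/W) ÷ [dose × (2.9/W)^0.33]:

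| Human weight (assumed) | 15 mg/kg (13 weeks) | 20 mg/kg (39 weeks) |
|---|---|---|
| 50 kg | 1.36 | 1.02 |
| 60 kg | 1.21 | 0.91 |
| 70 kg | 1.09 | 0.82 |
| 80 kg | 1.00 | 0.75 |

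The last column is the middle one × 15/20. It assumes 2.9 kg for the 39-week animals, whose weight the protocol does not give.

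**6. What uses 3.43 mg/kg.** It yields 3.43/10 = 0.34 mg/kg, 0.34 × 70 = 24 mg, and so the 25 mg starting dose. Groups 1, 3, 4 and 5 receive 50, 200, 100 and 400 mg, and Group 2 receives no GS-9992. In 1.4.1, 50 and 100 mg rest on 12-week ACHIEVE results, and 200 mg on that trial's safety board review. For 400 mg the text cites the exposure ratios, 7 or 12 days of dosing at 400 mg in patients with hepatitis C, 7 days at more than twice that dose, and confirmation of Group 3 safety through Week 12. Section 6.11 adds a hold rule for Group 5. No endpoint, visit, rule or analysis in the protocol or SAP takes 3.43 mg/kg as an input.

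**The case for a change.** The strongest case for a change is that the error can be checked from one section, that correcting it costs only wording, and that it touches the drug's one target organ. By inference the exposure ratios come from the 13-week study, because the 39-week exposures are unreported. If so, the same 15 mg/kg/day NOAEL gives a reassuring comparison by exposure and a ratio of about one or above by body surface, and the Group 5 reader is shown only the first. Section 1.2.3 reports liver findings from 30 mg/kg/day, twice that NOAEL.

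Part of this stands. Equation 1 is not what it is called, the human-equivalent doses do not come from one stated method, and the study behind the 3.5- and 1.7-fold ratios is not named.

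The rest is weaker. Exposure and mg/kg comparisons are different metrics and can differ without contradiction. The protocol does compare 400 mg with a NOAEL, using measured exposure. It also prints both 3.43 mg/kg and the mg/kg equivalent of 400 mg in the Groups 1-4 text, so a reader can make the other comparison. The body-surface result is too dependent on assumptions to carry a finding: the 39-week NOAEL alone moves most of the ratios below one, although that study is still being reported. Setting both metrics out for every dose would be additional reporting.

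**Conclusion.** This is a clerical fault in background rationale, and no change to the plan follows. The inconsistency is established: 3.47 against 3.43 mg/kg for the monkey, 2.90 and 3.43 against 2.5 to 5 for the woodchuck, and 0.70 against 0.62 for the mouse. Under the assumed weight-ratio scaling at 70 kg, the printed human-equivalent NOAEL is about 35% too low (3.43/5.25 = 0.65), so the printed figure makes 400 mg look further above the NOAEL (1.67 times) than the rescaled one does (1.09 times).

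No group's dose is shown to depend on the figure. The 400 mg ratios, 1.36 to 1.00 or 1.02 to 0.75 over 50 to 80 kg, rest on an assumed formula, assumed human weights and, for the second range, an assumed animal weight. They support no firm statement in either direction. The conversions in 1.4.1 disagree with one another and would need to be reconciled if that text is reissued, but this is editorial and leaves the design, conduct and analysis as they are. No dose is judged or proposed here.

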### **GS-9992 for Group 5 (400 mg)**

GS-9992 (aka inarigivir and SB 9200), developed by Spring Bank Pharmaceuticals, is a prodrug of SB 9000, which consists of two diastereomers Rp-9000 and Sp-9000 for the treatment of hepatitis B virus (HBV) infection. *In vitro* and *in vivo* studies have established that both forms of SB 9200 have antiviral activity against HBV and HCV ribonucleic acid (RNA) viruses. Upon oral administration, both prodrug SB 9200 isomers are equivalently converted to their active dinucleotide metabolites SB 9000 by esterases. Phase 1 clinical testing is complete, and a 12-week Phase 2 study (SBP-9200-HBV-201) is currently ongoing in HBV-infected patients. The safety and pharmacokinetic profile of SB 9200 and its active diastereomer metabolites have been extensively characterized in healthy subjects and patients. Both the pharmacokinetic properties and accumulated pre-clinical and clinical safety of all active moieties of SB 9200 support extended administration of 400 mg in the target patient population (reference SB 9200 IB).

*In vitro* binding studies showed dose-dependent binding of SB 9200 and SB 9000 to RIG-1 and equipotent activity of Rp and Sp isomers of SB 9000. Additionally, *in vitro*, SB 9000 demonstrated a dose dependent reduction in viral replication in either primary human hepatocytes or HepG2.2.1.5 cells infected with HBV with EC50 ranging from 0.2  $\mu$ M to 2  $\mu$ M depending on treatment duration. To connect the inarigivir concentrations that were seen to be active *in vitro* to the clinical setting it is necessary to consider that inarigivir and SB 9000 are found to concentrate in the liver at levels greater than 20-fold as compared to the plasma as was shown in rat distribution studies and when inarigivir levels were measured in the rat following repeated administration. The plasma Cmax values of SB 9000 observed in the DDI study (SBP-9200-HBV-202) at 400 mg were 11.19 ng/ml and assuming similar concentrative activity of SB 9000 in the liver of humans as was observed in the rat there would be liver concentrations of SB 9000 of approximately 405 nM at the time of maximal concentration. Anti-viral activity of SB 9000 was observed *in vitro* in various test systems at concentrations below and above this value.

*In vivo* pharmacology studies following IP injection of 100 mg/kg/day showed significant reduction of viral DNA load in the liver of transgenic mice, with antiviral activity similar to that of adefovir.

The minimally effective dose in this model was 1 mg/kg. Similar studies conducted with oral SB 9200 showed the minimal effective dose to be between 1 and 10 mg/kg. Other, in vivo studies in naturally infected (WHV) woodchucks showed induction of RIG-1 in liver biopsies after 12 weeks treatment, with dose-dependent activity following 12 weeks of 15 and 30 mg/kg/day resulting in reduced surface antigen and serum WHV DNA; delayed viral relapse at higher dose; elevated IFN, RIG-1, NOD2; and significant reductions in hepatic viral DNA, RNA, cccDNA. Although the pharmacokinetics of SB 9000 were not measured in the pharmacology studies, the lowest doses of SB 9200 shown to have efficacy in these pharmacology models were 10 mg/kg/day in the mouse and 15mg/kg in the woodchuck, on the basis of body surface area, the human equivalent doses of either the mouse or the woodchuck would be adequately covered by a 400 mg/day dose in humans.

The pre-clinical and clinical profile of inarigivir supports its exploration as a potential treatment option for patients with HBV at 400 mg. The pre-clinical toxicology studies have consistently indicated that the monkey is the more sensitive species and that the liver is the sole target organ of inarigivir mediated toxicity. The exposure parameters Cmax and AUC(0-t) at the identified NOAEL in the longest term completed GLP toxicology study are 3.5 and 1.7-fold higher respectively than those observed when 400 mg was administered in the clinic. In all of the clinical studies conducted so far where doses between 25 and 900 mg have been administered daily for durations between 7 days and 12 weeks, the safety profile has been acceptable and there have been no changes in liver safety parameters that were independently associated with inarigivir, instead the changes in liver enzyme levels to date have been correlated with immune flares consistent with an ongoing HBV infection.

The clinical safety of a 400 mg daily dose of inarigivir in HCV patients has been tested in two different studies for durations of either 7 or 12 days and demonstrated a benign safety profile in each case. Additionally, inarigivir has been shown to be well tolerated at doses more than 2-fold greater than the target dose of 400 mg QD for 7 consecutive days. In the ongoing ACHEIVE Ph 2 study (SBP-9200-HBV-201), HBV patients have been administered up to 200 mg daily for 12 weeks with a similar benign safety profile as was observed in the shorter-term studies. The clinical pharmacokinetics of inarigivir and its primary active metabolites Sp-9000 and Rp-9000 have demonstrated predictable and linear PK over a dose range of 25-900 mg. Accumulation of its active metabolites is minimal following multiple dose administration and the change in exposure with dose is consistent with dose proportionality. In the Ph1 study (SB12-9200-101), a statistically significant relationship between SB 9200 Cmax at steady-state and maximum suppression of HCV RNA on Day 7 was observed (p=0.015). In the HCV trial (SB12-9200-101), the peak individual viral load drop was observed to improve from 1.5 to 1.9 log10 when the dose of SB 9200 increased from 200 to 400 mg. Further dose increases did not result in response increases. In the ongoing Ph 2 study (SBP-9200-HBV-201) in CHB patients, at doses between 25 and 100 mg there was an observed dose response in anti-viral clinical activity without an as yet observed plateau, indicating that higher doses could have increased levels of efficacy. This observation parallels with the observed dose proportionality of the plasma pharmacokinetics of inarigivir. Based on these observations it is proposed that a 400 mg daily dose administered to patients with HBV would lead to plasma and liver levels of inarigivir consistent with increased activity on the hepatitis B virus infection as well as a benign safety profile. To further ensure safety of the administration of GS-9992 400 mg plus TAF for 12 weeks in Group 5, safety data of 200mg GS-9992 plus TAF through Week 12 in all subjects enrolled in Group 3 will be confirmed by the Medical Monitor prior to enrollment of Group 5.

